		11.3.1 REDCap confidentially	
12	Data	Handling and Record Keeping	
	12.1	Data Capture Methods	
	12.2	Types of Data	59
	12.3	Storage of data	
	12.4	Study Records Retention	60
	12.5	Protocol Deviations	
13	INSU	RANCE & Finances	62
14	Public	cation Policy	63
15		ture References	
16	Appe	ndix	68
		C Serious Adverse Event Form	
	REDO	Cap Pre-screening questionnaire	72

LIST OF ABBREVIATIONS

ACL Australian Clinical Labs

AE Adverse Event/Adverse Experience

BAI Beck Anxiety Inventory

BIS-11 Barratt Impulsivity Scale version 11
CBT Cognitive Behavioural Therapy

CGI - I/S Clinical Global Impression scale - improvement/severity

CRF Case Report File

CTC Clinical Trial Coordinator

DQES v2 Dietary questionnaire for epidemiological studies version 2

ERP Exposure response prevention

GCP Good Clinical Practice

GMP Goods Manufacturing Practice
HAM-D Hamilton depression rating scale

ICH Requirements for Pharmaceuticals for Human Use

IEC Independent Ethics Committee
IICF Informant Information Consent Form

IP Investigational Product
IRB Institutional Review Board

N Total number of participants in population

NAC N-acetylcysteine

OCD Obsessive-Compulsive Disorder

PGI – I/S Patient Global Impression scale - improvement/severity

PI Principal Investigator

PICF Participant Information Consent Form

RA Research assistant

RCT Randomised, controlled trial

SAFTEE Systematic assessment for treatment emergent side effects SCID-5-CT Structured clinical interview for DSM-5 Clinical Trial version

SDS Sheehan Disability Scale

SNP Single nucleotide polymorphisms
SOP Standard Operating Procedure
TR-OCD Treatment refractory OCD

WHOQOL-BREF World Health Organisation Quality of Life-BREF Y-BOCS Yale-Brown Obsessive-Compulsive Scale

......

PROTOCOL SUMMARY

Title: N-acetylcysteine augmentation (NAC) in Obsessive-Compulsive disorder (OCD): A 24 week, randomised, double blind, placebo controlled trial

Phase: III

Population: Male and female adults (18-75 years old) with Obsessive-Compulsive Disorder (N = 200) located in Australia.

Number of Sites: (3) The University of Melbourne (The Melbourne Clinic); The University of Queensland (Royal Brisbane and Women's Hospital); Western Sydney University (National Institute of Complementary Medicine; NICM)

Study Duration: 2016 - 2019

[figure not shown]
Subject Participation Duration: 24 weeks

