8 STATISTICAL CONSIDERATIONS

8.1 Sample Size Considerations

A sample size of 200 participants (100 participants in each arm) are to be recruited and intention-to-treat principles will be applied to all data. A large sample of 200 participants is powered to detect a potential small to moderate effect size (f = 0.15) difference between NAC and placebo beyond treatment as usual, approximating a clinically significant 3 point reduction on the YBOCS (using all post-baseline data via intention-to-treat analysis). Based on an ANOVA model over seven time-points, a two tailed analysis with alpha=0.05, beta=0.80, and a critical F of 3.78; 200 participants (not including drop-outs) are required to detect a small to moderate effect size difference in Y-BOCS scale score between treatment and placebo.

The primary efficacy analysis will assess mean treatment group differences for the primary outcome measure (Y-BOCS) using a mixed-effects model, repeated measures approach (MMRM). Results from the analysis of dichotomous data (e.g. demographics data) will be presented as proportions with 95% confidence interval, and Fisher's Exact *p*-value where appropriate. Analysis of covariance (ANCOVA) will also be used to compare differences between treatment means in changes from baseline to week 20 last observation carried forward (LOCF) endpoint. The ANCOVA model will assess confounding covariates including intervention type (medication or psychological care), as well as age, gender, weight, physical activity levels, smoking and alcohol consumption.

Non-parametric statistics will be used when assumptions for parametric methods are violated. Effect sizes will be calculated using Cohen's d. All tests of treatment effects will be conducted using a two-tailed alpha level of 0.05 and 95% confidence intervals. Data will be analysed via SPSS 23.0.

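### Section 8.1 requires 200 participants net of drop-outs but recruits only 200, so its 80% power is not supported on the paragraph's own terms once participants withdraw

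*Protocol*

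**What the plan says.** Section 8.1 gives the recruitment target first: "A sample size of 200 participants (100 participants in each arm) are to be recruited". The Protocol Summary gives the same total for the trial population: "Obsessive-Compulsive Disorder (N = 200) located in Australia".

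Further down the same paragraph, section 8.1 gives the number that the calculation calls for: "200 participants (not including drop-outs) are required to detect a small to moderate effect size difference in Y-BOCS scale score".

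The inputs stated are an effect size ("powered to detect a potential small to moderate effect size (f = 0.15) difference between NAC and placebo"), its translation into points ("approximating a clinically significant 3 point reduction on the YBOCS"), the model ("Based on an ANOVA model over seven time-points") and the error rates ("a two tailed analysis with alpha=0.05, beta=0.80, and a critical F of 3.78"). The protocol states neither a correlation between visits nor an expected drop-out rate, and it has no rule for over-recruitment or replacement.

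The primary analysis in section 8.1 is a mixed model for repeated measures (MMRM), by intention to treat, on all post-baseline data. Section 4.3.3 lists the events that lead to withdrawal. Section 5.13 asks for a Y-BOCS at the withdrawal visit if the participant is willing, and lets a withdrawing participant have all data destroyed and left out of the analysis.

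**The concern.** One figure serves two purposes. As a requirement, 200 excludes drop-outs; as a recruitment target, 200 includes them. Over 24 weeks, with the withdrawal rules of section 4.3.3, some attrition has to be expected. Entry is allowed up to a Y-BOCS of 31 and withdrawal is triggered at 32, so for some participants a one-point worsening is enough.

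At stake is how a null result would be read. Section 2.2.2 reports that two of the four earlier adult trials showed no significant effect at their endpoint. If this trial is also null, readers will weigh that against the power stated here, and on the paragraph's own wording that power assumes complete retention.

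**Working it through.** **Inputs from section 8.1.** f = 0.15 (Cohen's d = 2f = 0.30); m = 7 time points; two arms, N = 200; two-sided alpha 0.05. The stated beta of 0.80 is read as power of 80%.

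**Inputs assumed.** Between-visit correlation rho = 0.5, with 0.3 to 0.8 shown as a range. Drop-out of 10% to 30%.

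**Step 1: reproduce the 200.** For the between-group effect in a repeated-measures ANOVA, the noncentrality is lambda = f² × N × m / (1 + (m − 1) × rho), referred to a noncentral F with 1 and N − 2 degrees of freedom.

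- lambda = 0.0225 × 200 × 7 / (1 + 6 × 0.5) = 31.5 / 4 = 7.875.
- The critical F(1, 198) is 3.89, and power is 79.7%. Power of 80% is first reached at N = 202 (even totals).

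So 200 is reproduced to within rounding. Of the variants tried, only the between-group effect with rho near 0.5 comes close. The group-by-time interaction would need 46 participants, and a single-endpoint comparison at d = 0.30 would need 175 per arm.

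**Step 2: worst case.** If drop-outs contribute nothing, which is how the parenthesis in section 8.1 counts them, replace N by 200 × (1 − d).

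| Drop-out (assumed) | N left | lambda | Power |
|---|---|---|---|
| 0% | 200 | 7.875 | 79.7% |
| 10% | 180 | 7.09 | 75.4% |
| 20% | 160 | 6.30 | 70.4% |
| 30% | 140 | 5.51 | 64.5% |

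**Step 3: planned analysis with partial data.** Assume compound symmetry with rho = 0.5, drop-out that is monotone and spread evenly over the visits, and an effect that is the same at every visit. A participant with k measurements contributes k / (1 + (k − 1) × rho): 1.75 for all seven, 1.60 for four, 1.00 for one. Then lambda = f² × N × (average contribution).

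| Drop-out (assumed) | Average contribution | lambda | Power |
|---|---|---|---|
| 10% | 1.722 | 7.75 | 79.1% |
| 20% | 1.694 | 7.62 | 78.4% |
| 30% | 1.666 | 7.50 | 77.8% |

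The loss against step 1 is then 1 to 2 points, because with rho = 0.5 the later measurements add little to the earlier ones.

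**Step 4: sensitivity to rho, no drop-out, N = 200.** Power is 91.6% at rho = 0.3, 85.7% at 0.4, 79.7% at 0.5, 74.0% at 0.6 and 64.0% at 0.8. The unstated correlation moves the result more than the drop-out rate does.

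**Step 5: the stated critical F.** Section 8.1 gives 3.78; alpha 0.05 with 1 and 198 degrees of freedom gives 3.89. With 3.78 the power at N = 200 is 80.5%. The reconstruction is therefore close to the protocol's calculation but not identical to it.

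**The case against.** The strongest reply is that the protocol does not discard drop-outs. Section 8.1 plans intention-to-treat analysis of all post-baseline data by MMRM, and section 5.13 tries to collect a final Y-BOCS at withdrawal. On that footing the loss is the 1 to 2 points of step 3. This largely stands, and it rules out reading the 64% to 75% range as the power of the trial: that range is the worst case.

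The reply has limits. Step 3 gives full credit to every measurement, including the first. Non-responders are titrated only from week 8 (section 5.2), so a benefit that builds late would leave early partial data with less information. Early drop-out acts in the same direction, and data destroyed on request contribute nothing to any model. Nor does MMRM remove the contradiction. If partial data were meant to count, the parenthesis is wrong; if 200 completers were meant, recruitment is short.

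A second reply is that the calculation need not sit on the 80% line. This also stands. A reader might infer that power falls below 80% as soon as one participant leaves, but that holds only near the back-fitted rho of 0.5. With rho = 0.4, even discarding 10% of participants leaves 81.9%.

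Third, section 4.3.3 is less absolute than its length suggests. A SIGHD-17 total of 24 or more, deterioration of OCD, serious side effects and interacting medication are left to the judgement of medical monitors or investigators. The drop-out rate therefore cannot be inferred from the list.

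**Conclusion.** The contradiction is in the text and needs no assumption: 200 after drop-out and 200 recruited are incompatible unless retention is complete. The stated 80% is therefore not supported on the paragraph's own terms.

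The size is conditional. At rho = 0.5 and 10% to 30% drop-out, power lies between the worst case (75% to 64%) and the planned MMRM under favourable simplifications (about 79% to 78%). Both the correlation and the drop-out rates are assumptions.

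Two stronger conclusions are not supported. One is that 20% attrition leaves about 70% power among those with week-20 data. The 70% refers to an effect averaged over seven measurements in 160 complete cases. A comparison at week 20 alone with d = 0.30 has about 56% power at N = 200 and 47% at N = 160, while the MMRM with partial data gives about 78% at 20% drop-out. The other is that the trial must enrol more. No drop-out rate is documented, and the loss under the planned analysis may be small.

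This should be fixed. It is a flaw in how the power is justified, and it does not invalidate the design or the analysis.

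**What to change.** Keep recruitment at 200 and amend section 8.1 as follows:

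- Delete the parenthesis about drop-outs and state that 200 is the number randomised.
- State an expected attrition rate, for example from the blinded pooled attrition to date, and a between-visit correlation, each with a short justification.
- Restate the power for the planned MMRM under those two values, and name the contrast to which it applies (an average over visits or a single visit).
- Give the complete-case figure for the same contrast and correlation as a lower bound.
- While the paragraph is open, correct beta = 0.80 to power = 0.80 and reconcile the critical F of 3.78 with alpha 0.05.

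The cost is one paragraph of wording, with no extra patients and no change to conduct or analysis. The stated power becomes slightly less favourable. If the sponsor does want 200 participants after drop-out, recruitment would have to be 200 / (1 − d): 223 at 10%, 250 at 20% and 286 at 30%.

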placebo + fluvoxamine over 10-weeks (Paydary et al., 2016). A third RCT was conducted in Brazil involving 40 adult patients who had failed to respond to at least one SSRI or clomipramine trial lasting for minimum 12 weeks (Costa et al., 2017). All participants experienced a reduction in their OCD symptoms (as per the Y-BOCS), however, NAC (3,000mg per day maximum dose from week-3 of the study) was not significant over placebo at the end of the 16-week intervention. In addition, our own pilot study (N = 44) published in 2015 revealed a non-significant effect for 3,000mg of NAC over placebo after 16-weeks (Sarris et al., 2015). A significant effect for improving compulsive symptoms was observed at week-12, however, this effect dissipated by week-16 end point. Our sample included participants with ranging severities and chronicity of OCD, and a post-moderator analysis revealed that NAC was more beneficial in less chronic presentations of OCD (<17 years duration), as well as those who were under the age of 34 (Sarris, Oliver, Camfield, & Dean, 2016). Further, previous clinical trials have revealed that NAC at doses beyond 3,000mg have elicited symptom improvement in attention-deficit hyperactivity disorder (ADHD), as well with lengthier administration of NAC (up to 6 months) in bipolar disorder (Berk et al., 2008; Berk et al., 2012; Garcia et al., 2013). Given these findings, and the many questions which remain regarding the benefits of NAC for differing symptom dimensions of OCD, treatment status, gender and required dose, a larger scale study to provide power to investigate these facets is warranted.

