5.2 Dosage, Preparation and Administration of Study Intervention/Investigational Product

All participants will commence the IP at a dose of two capsules, twice per day for the first eight weeks. The IP will be advised to be taken at least one hour away from other medications and after food, with water or orange juice and minimum of five hours between IP doses. All doses will be taken orally.

In cases of non-response (determined by < 35% reduction in Y-BOCS score from baseline), participants IP will be titrated by 500mg BID (1,000mg per day) from week-8, up to a maximum dose of 4,000mg per day (for example, see table 5.1 below). Note, participants may only increase their dose by 1,000mg per day and remain on this dose for the following four weeks before reassessing response and tolerance at the next study visit. If side effects are current/ongoing at a time point where titration may occur, for example, week-8, the medical investigators will determine if titration is appropriate for the participant. In the event that titration does occur, the RA will call the participant one week later to ensure tolerance to the higher dose. The medical investigators will be notified of any reported side effects and will determine if appropriate for the participant to continue on the titrated dose, or return to the previous tolerable amount.

Table 5.1 Example titration strategy of IP in cases of non-response* reported at each study visit

Visit period	Number of	Dose of IP/day	Containers
	capsules		required
Baseline → Week-4	2 BID	2,000mg	1 x 120c
Week-4 → Week-8	2 BID	2,000mg	1 x 120c
Week-8 → Week-12*	3 BID	3,000mg	2 x 120c
Week-12 → Week-16*	4 BID	4,000mg	2 x 120c
Week-16 → Week-20*	4 BID	4,000mg	2 x 120c

Note *In cases of non-response (<35% reduction in Y-BOCS score from baseline) participants may increase the dose of IP by 1,000mg per day from these time points. Conversely, participants may reduce the dose of IP in the event of intolerable side effects, as determined by the participant or medical investigators.

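### The additional Week-20 ANCOVA carries last observations forward without justification and can misstate the treatment difference in either direction; the primary MMRM is not affected

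*Protocol*

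**What the plan says.** Section 8.1 names the MMRM as the primary efficacy analysis of the Y-BOCS and attaches no visit to it. It then adds an ANCOVA comparing the arms on "changes from baseline to week 20 last observation carried forward (LOCF) endpoint", and uses the same model to examine covariates such as age, gender and type of concurrent treatment. No reason is given for LOCF. The hypothesis in section 3.1 lists six post-baseline visits and singles out none.

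Four other places bear on what would be carried forward:

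- **Section 4.3.3** withdraws participants from the study for, among other reasons, a Y-BOCS of 32 or more, more than 7 consecutive days off product, serious side effects and substantial treatment changes.
- **Section 5.13** collects a Y-BOCS at the withdrawal visit only if the participant is willing.
- **Section 5.2** states: "All participants will commence the IP at a dose of two capsules, twice per day for the first eight weeks". From Week 8 the dose may rise for those with less than a 35% reduction in Y-BOCS. In the Table 5.1 example the highest step is first assessed at Week 16.
- **Section 2.2.2** says of one earlier 16-week trial: "All participants experienced a reduction in their OCD symptoms (as per the Y-BOCS"). It also reports that in the investigators' own pilot an effect on compulsive symptoms at Week 12 had gone by Week 16.

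**The concern.** LOCF enters a participant's last available score as though it had been measured at Week 20. That is harmless only if the score would not have moved afterwards, or if any movement cancels between the arms. This protocol gives reasons to doubt both. The cited studies show scores and effects changing over time. Treatment intensity changes for non-responders after Week 8. Some exits are triggered by the outcome itself, and the exit score may be absent, so that an older one is carried.

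At stake is the one efficacy comparison in section 8.1 with a named visit. Because the MMRM is given no visit, a reader looking for the Week-20 result is likely to go to the LOCF figure.

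**Working it through.** **The plan's own figure.** Section 8.1 gives "A sample size of 200 participants (100 participants in each arm"), f = 0.15 and seven time points, with a target "approximating a clinically significant 3 point reduction on the YBOCS". For the between-group test in a repeated-measures ANOVA, with an assumed correlation of 0.5 between visits:

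- λ = f²·N·m / (1 + (m−1)ρ) = 0.0225 × 200 × 7 / (1 + 6 × 0.5) = 31.5 / 4 = 7.875
- Power at N = 200 is 0.7975, and N for 80% power is 202.

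The 200 is therefore reproduced to within rounding, although the printed critical F of 3.78 is not: F(0.05; 1, 198) = 3.889. The sample size belongs to the repeated-measures analysis, not to the LOCF ANCOVA.

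**Inputs for LOCF.** The protocol gives the visits (Weeks 4, 8, 12, 16, 20) and the 3-point target. It gives no drop-out rate and no expected trajectory. Assumed: drop-outs follow their arm's mean course until they leave; their last visit is spread evenly over Weeks 4 to 16; improvement is linear to Week 20 unless stated otherwise.

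**Formula.** Let I be the mean improvement at Week 20, d the drop-out fraction, and q the mean fraction of I reached at the carried visits. The LOCF mean in an arm is I × (1 − d(1 − q)). With linear improvement, q = (0.2 + 0.4 + 0.6 + 0.8)/4 = 0.5.

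**Placebo improves 6 points; drop-out NAC 30%, placebo 15%**

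- No true effect: 6 × 0.85 − 6 × 0.925 = 5.10 − 5.55 = −0.45, that is, 0.45 points against NAC.
- No true effect, all drop-outs last seen at Week 4 (q = 0.2): 6 × 0.76 − 6 × 0.88 = −0.72.
- True benefit 3: 9 × 0.85 − 6 × 0.925 = 7.65 − 5.55 = 2.10.

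**Equal drop-out** (the placebo course cancels)

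- 15%, effect growing linearly: 3 × 0.925 = 2.78.
- 30%, effect growing linearly: 3 × 0.85 = 2.55.
- 30%, effect starting only after Week 8 (q = (0 + 0 + 1/3 + 2/3)/4 = 0.25): 3 × (1 − 0.30 × 0.75) = 2.32 to 2.33.
- Any equal rate, effect complete by Week 4: exactly 3.0.
- Any equal rate, no effect: exactly 0.

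**Reversed drop-out, NAC 15%, placebo 30%; placebo improves 5 points**

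- Effect growing linearly: 8 × 0.925 − 5 × 0.85 = 7.40 − 4.25 = 3.15.
- Effect complete by Week 4: 3 + 5 × (0.925 − 0.85) = 3.375, about 3.38.

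**An effect that fades.** If the arms differ at the carried visits but no longer at Week 20, equal drop-out d leaves d times the average earlier difference in the LOCF result. LOCF then overstates benefit.

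**Type I error by simulation** (100 per arm, SD 6, correlation 0.6, baseline Y-BOCS as covariate; all assumed):

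| Drop-out NAC / placebo | Both arms improve 5 points | Both arms improve 8 points |
|---|---|---|
| 0% / 0% | 0.051 | 0.046 |
| 30% / 30% | 0.049 | 0.050 |
| 30% / 15% | 0.082 | 0.131 |
| 15% / 30% | 0.078 | 0.124 |
| 40% / 10% | 0.195 | 0.361 |

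**The case against.** The strongest reply is that the primary analysis does not use LOCF. Section 8.1 ranks the two analyses, so a different ANCOVA result would not leave the trial without a primary answer. This stands. A reader might infer that the main efficacy result is biased, or that the plan contradicts itself; neither follows from an additional analysis with a different missing-data assumption.

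Further points on that side also hold:

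- **Direction.** One might infer that LOCF always works against NAC. It does not: reversed drop-out, or an effect that fades as in the pilot, inflates the difference.
- **Drop-out.** Higher loss on NAC is not established. Section 2.3.1 lists gastrointestinal effects but says that few participants in earlier psychiatric studies withdrew because of side effects.
- **Trajectory.** Improvement in both arms is reported for one earlier trial, in patients who had not responded to prior medication. This protocol excludes treatment-refractory OCD and predicts no course.
- **Which score is carried.** Someone withdrawn at a Y-BOCS of 32 or more may carry a current, worsened score rather than an early, favourable one.
- **Titration.** Only non-responders move up. For responders an early score is not from a lower dose than their Week-20 dose.
- **Standard errors.** LOCF might be said to understate uncertainty here as well. With equal drop-out and no effect, the simulated error rate stays at about 0.05, so the working does not show this.

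What the reply leaves untouched is that LOCF is stated without a reason, and that its error depends on quantities nobody knows in advance.

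**Conclusion.** The point holds for the additional ANCOVA only. Its LOCF endpoint is unjustified and unlabelled, and it can misstate the Week-20 difference in either direction when drop-out differs by arm or the effect changes over time. There is no bias with equal drop-out and either no effect or an effect already complete at the carried visit, provided drop-outs follow their arm's mean course.

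In the illustrations, a true 3 points becomes anything from about 2.1 to about 3.4, and a null effect becomes up to 0.45 points (0.72 if all drop-outs leave after Week 4) against NAC. All of these sizes rest on assumed drop-out and trajectories. They show what is possible and do not forecast this trial. The weakness is worth correcting, but it does not threaten the primary result.

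**What to change.** In section 8.1, state that the Week-20 treatment effect is the Week-20 contrast from the MMRM, using all observed visits. Remove the LOCF ANCOVA, or keep it only as a labelled sensitivity analysis. If a separate Week-20 ANCOVA is wanted, run it on multiply imputed data with adjustment for baseline Y-BOCS.

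The cost is wording and modest programming; no new visits, data or participants are needed. Comparability with older LOCF reports is reduced. If the ANCOVA goes, the covariate assessment that section 8.1 assigns to it must move to the MMRM. The MMRM has its own assumption, that missingness depends only on observed data. Outcome-triggered withdrawals fit this better when the triggering Y-BOCS is recorded and included in the model.
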